Effect of immune-enhancing enteral nutrition formula enriched with vegetable derived *n-3* fatty acids on NK cell activity in hospitalized patients for rehabilitation

NCT number : In Progress (not assigned)

Date of the document : March, 2018.

Materials and Methods

Participants

From August 2015 to March 2018, ninety-four patients were enrolled in this study after admission to the department of rehabilitation at Yonsei University Severance Hospital. Yet, thirty-four subjects discontinued the study for personal reasons (withdrawn consent for clinical trial, move to another department or hospital, other disease treatment, Nil Per Os, etc.). There were no serious adverse effects for the withdrawal reasons. Results of this study were analyzed with sixty subjects, except for the dropouts. Majority of patients were forty-three quadriplegia patients and five hemiplegia patients with cerebellar pathophysiological origin. Eleven patients with ataxic quadriparesis and one patient with lateral medullary syndrome trauma were also enrolled. There was no difference between two groups regarding diagnostic distribution ($p=0.100$, chi-square test). Informed consent was provided by patients or their close family member. This investigation was approved by the Institutional Review Board at Yonsei University Severance Hospital, Seoul, Korea (Approval number: 2015-0907). All comorbidities and histories of the study participants were recorded under IRB tracking number.

Randomization and Intervention

Using computer-generated randomization lists, ninety-four patients were randomized to receive one of two types of enteral nutrition: soybean enteral nutrition (control), vegetable (canola, flaxseed) derived *n*-3 fatty acid enriched enteral nutrition (n3EN). The ready-to-use soybean used formula and n3EN formula had identical packaging with no differences in appearance, texture, or smell. Patients assigned to the control group received a soybean used formula by tube feeding. Those assigned to the n3EN group received vegetable *n*-3 fatty acid

enriched formula by tube feeding (product; Yonsei Dairy Co., Seoul, South Korea). The composition of both control and test group enteral formula shown in Table 1. The nutrient (fatty acids) composition of Canola, Flaxseed and Soybean oil by *United States Department of Agriculture database* (25) attached as supplemental data (Supplemental table 1).

Enteral nutrition was initiated within 24 h of admission. Enteral feeding was delivered at a constant rate to achieve a minimum of 50% basal energy expenditure (BEE; determined using the Harris–Benedict equation) $\times 1.2$ within the first 12 h. If well tolerated, enteral nutrition was advanced to achieve a BEE $\times 1.2$ within 48 h. Complementary feeding with enteral or parenteral nutrition was allowed for an initial 48 h. From the third day, the patient received a minimum of 75% of BEE $\times 1.2$. The daily enteral intake was recorded to obtain the total volume and calories delivered to the patients. The data on daily total calorie intake were abstracted from the medical records.

Anthropometric Parameters and Blood Collection

The subjects' gender, age, height (cm), weight (kg), weight change were tracked. Body weight during hospital stay was derived from the medical records on the first day and 14 days after consumption of each formula and was used to calculate BMI (Body Mass Index = body weight (kg) / height (m²)) (26). Venous blood specimens were collected in EDTA-treated and plain tubes and centrifuged to obtain plasma and serum. The collected blood samples were stored at $-70\text{ }^{\circ}\text{C}$ until analysis.

Hematology and biochemical analysis

Serum glucose concentrations were measured according to the hexokinase method on

a Hitachi 7600 autoanalyzer. Serum albumin concentrations were analyzed through the BCG method using an ALB kit (Siemens, Tarrytown, NY, USA) with an ADVIA 2400 auto-analyzer (Siemens, Tarrytown, NY, USA). Leukocyte count was determined using the HORIBA ABX diagnostic analyzer (HORIBA ABX SAS, ParcEuromedecine, Montpellier, France). Serum high-sensitivity C-reactive protein (hs-CRP) levels were measured with a kit from the N-Assay LA CRP-S D-TYPE (Nittobo, Tokyo, Japan) with a Hitachi 7600 autoanalyzer.

Cytokine Assay in Serum

Interferon (IFN)- γ was measured with a kit from an IFN gamma High-Sensitivity Human ELISA Kit (Abcam plc-Cambridge Science Park, Cambridge, UK) according to the manufacturer's instructions. Interleukin (IL)-12 levels were analyzed by a High-Sensitivity Human IL-12 (P70) ELISA kit (Genway Biotech Inc., San Diego, CA, USA) using a Victor \times 5 2030 multi label plate reader (PerkinElmer, Hopkinton, MA, USA) at 450 nm. IL-6, IL-1 β , and tumor necrosis factor (TNF)- α levels in serum were measured using the Bio-PlexTM Reagent Kit (Bio-Rad Laboratories, Hercules, CA, USA).

NK Cell Activity

Isolated PBMCs (peripheral blood mononuclear cells) from the whole blood samples were incubated with K562 cells to analyze the cytotoxic activity of NK cells. A whole blood sample was mixed with the same volume of RPMI medium 1640 (Gibco, Thermo Fisher Scientific, Waltham, MA), then gently overlaid on Histopaque[®]1077 (Sigma-Aldrich, Irvine, UK) and centrifuged for 20 min at 1800 rpm at 15 °C. After separation, a buffer coat layer was isolated, washed once with RPMI 1640 medium, and then resuspended in 1 mL of 10% fetal

bovine serum. The isolated PBMCs (effector cell, E) were seeded into 96-well plates at ratios of 10:1, 5:1, 2.5:1, 1.25:1 and 0.625:1 with the K562 cells (target cell, T) and then incubated at 37 °C under 5% CO₂ for more than 4 h. The cytolytic activities of NK cells were analyzed via the CytoTox 96® Non-Radioactive Cytotoxicity Assay Kit (Promega Co., Fitchburg, WI, USA) according to the manufacturer's instructions. The color reactions were read at 490 nm using a Victor ×5 2030 multi label plate reader (PerkinElmer, Hopkinton, MA, USA), and the results were calculated by the following formula:

$$\% \text{ Cytotoxicity} = (\text{Experimental-Effector Spontaneous-Target Spontaneous}) / (\text{Target Maximum-Target Spontaneous}) \times 100$$

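### 94 patients were randomised but only the 60 who did not drop out were analysed; the other 34 (36.2%) are excluded with no dropout by arm, no missing-data method and no sensitivity analysis

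*Combined protocol and SAP*

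**What the plan says.** All references are to the combined protocol and SAP, Materials and Methods.

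- **Randomised set** (Randomization and Intervention): "ninety-four patients were randomized to receive one of two types of enteral nutrition".
- **Losses** (Participants): "thirty-four subjects discontinued the study for personal reasons". The examples begin with withdrawn consent and go on to "move to another department or hospital, other disease treatment, Nil Per Os", closing with an open-ended etc. They are listed for both arms together and without counts.
- **Analysed set** (Participants): "Results of this study were analyzed with sixty subjects, except for the dropouts".
- **Safety of the losses** (Participants): "There were no serious adverse effects for the withdrawal reasons".
- **Comparability** (Participants): "There was no difference between two groups regarding diagnostic distribution", with p=0.100 by chi-square test.
- **Masking** (Randomization and Intervention): the two formulas had "identical packaging with no differences in appearance, texture, or smell".

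No section gives the number randomised, lost or analysed in each arm, the timing of losses, a method for missing outcomes, or a sensitivity analysis. No target effect is defined.

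**The concern.** Randomisation makes the two arms comparable as randomised. The stated rule removes every patient who discontinued, which is an event after randomisation. What remains is a comparison of those who stayed in, and randomisation no longer protects it.

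That would matter little if losses were few or plainly unrelated to outcome. Neither can be taken for granted. More than a third of patients are gone. Being made nil by mouth, being treated for another disease, or being transferred can each reflect how the patient was doing, even though all are grouped under a personal-reasons label. The rule applies to the results as a whole, so it affects every outcome analysed in the 60, including NK cell activity, the outcome named in the title.

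The title asks about an effect in hospitalised rehabilitation patients. Without by-arm counts, a reader cannot judge how far the 60-patient contrast answers that question.

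**Working it through.** **1. Reproduce the stated number.** Inputs from Participants: 94 enrolled (and, in the next section, 94 randomised) and 34 discontinued. 94 − 34 = 60, which matches the stated number analysed. Excluded: 34/94 = 36.2%.

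**2. Who does the diagnosis check describe?** The diagnoses in Participants are 43 quadriplegia, 5 hemiplegia, 11 ataxic quadriparesis and 1 lateral medullary syndrome. 43 + 5 + 11 + 1 = 60, not 94. The p=0.100 therefore appears to describe completers. It does not show that the randomised arms stayed comparable, and a non-significant test would not show balance in any case.

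**3. What the pooled 34 can hide.** The allocation is not documented, so assume 47/47. A 17 v 17 split is 36.2% in each arm. A 12 v 22 split is 25.5% v 46.8% (Fisher p=0.053). Both fit the document.

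**4. When the completer contrast is biased.** Let *p* be the dropout proportion in an arm and *g* the gap (completer mean minus dropout mean, in SD units). Within an arm, the completer mean exceeds the mean of all randomised patients by *p·g*. Hence

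bias = p₁g₁ − p₀g₀

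This is zero when the two products are equal, and not only when the dropout counts are equal.

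**5. Illustrations.** Assumptions: 47/47 allocation; unit SD; SE = √(1/c₁ + 1/c₀), where c is completers per arm; no true effect; rejection = P(|Z + bias/SE| > 1.96). The document gives no SD and no gap, so every gap below is assumed. Signs are dropped.

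| Dropouts | Gap | Bias | SE | Rejection |
|---|---|---|---|---|
| 17 v 17 | equal in both arms | 0 | 0.258 | 5.0% |
| 12 v 22 | 0.55 v 0.30 SD | 12/47×0.55 − 22/47×0.30 = 0.140 − 0.140 = 0 | 0.262 | 5.0% |
| 12 v 22 | 0.5 SD in both | (22−12)/47×0.5 = 0.11 SD | 0.262 | 6.9% |
| 17 v 17 | 0.5 SD in one arm, 0 in the other | 17/47×0.5 = 0.18 SD | 0.258 | 10.8% |
| 17 v 17 | 0.75 v 0.25 SD | 17/47×(0.75−0.25) = 0.18 SD | 0.258 | 10.8% |
| 12 v 22 | 1.0 SD in both | (22−12)/47×1.0 = 0.21 SD | 0.262 | 12.8% |

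A noticeable bias does not require the gap to be confined to one arm: the last two rows have a gap in both. Nor does unequal dropout imply bias, as the second row shows. These are examples, not bounds.

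**The case against.** The best case for the plan is that it is open about the exclusion and offers some reassurance. It states the number lost, gives reasons, reports no serious adverse effects among them, and used formulas that could not be told apart. Enrolment ran to March 2018 and the document carries the same date, so the attrition cannot be undone.

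Part of this stands. The safety statement and the masking make dropout driven by serious harm, or by knowledge of the formula, less of a worry. They do not cover non-serious intolerance or clinical course, and none of it is given by arm. That the losses are past limits the remedy to reporting and reanalysis; it does not remove the problem.

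It is also fair to say that the document defines no estimand. The effect in all randomised patients is inferred here from the title and the randomised design. For a patient whose feeding stopped, the missing outcome could mean NK activity after stopping, or NK activity had feeding continued. The fix has to say which.

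Two stronger readings are tempting and not supported. A reader might infer that the 60-patient result is biased, perhaps in favour of the n3EN formula. No outcome data, by-arm losses or gaps are given, so neither bias nor its direction is shown. A reader might also infer that the conclusions overstate what was found. The document contains no outcome results or conclusions, and the analysis sentence itself says that dropouts are left out.

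**Conclusion.** The point holds and must be fixed. By the document's own rule, 36.2% of randomised patients are left out, some for reasons that can reflect clinical course, and nothing given by arm lets a reader judge the consequence. The analysed set is disclosed but not named as a completer set, and its interpretation is not limited. The one comparability check appears to cover only the same 60 patients.

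The documented facts (94, 34, 60, and no by-arm counts) carry the conclusion without any assumption. The SD and rejection figures depend on an assumed allocation, assumed gaps and a normal approximation. They show only that the same pooled 34 is compatible with no bias and with a bias large enough to matter.

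**What to change.** Replace the analysis sentence in Participants with text such as:

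> Sixty of the 94 randomised patients completed the study; the results are a completer analysis and conclusions are limited to completers. Numbers randomised, discontinued (with reason and timing) and analysed are given by arm, and available baseline data of dropouts and completers are compared. For NK cell activity, at one named effector:target ratio and time point, the target effect is stated: all randomised patients in the arm assigned, saying whether a missing outcome means the value after feeding stopped or the value had feeding continued. A delta-adjusted tipping-point analysis is reported for randomised patients without an outcome, with delta applied to each arm separately and to both, over a stated range (for example −1 to +1 SD of the completers).

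The ratio and time point must be named because the NK Cell Activity section lists five ratios and no sampling time. The only timing given, "on the first day and 14 days after consumption of each formula", is for body weight.

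Where outcome values are usable for any of the 34, or recorded variables related to dropout (the document says that comorbidities and daily enteral intake were recorded), also report an analysis of all randomised patients in the arm assigned that uses them, under stated missing-data assumptions. Imputing from arm and baseline NK activity alone, in the same linear model, adds nothing to a baseline-adjusted completer analysis: the imputed values lie on the fitted line and return the same estimate.

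**Cost.** Modest analysis and reporting work from existing records, with no extra patients or blood. Disposition by arm, the completer label and the tipping-point range do not depend on recovering missing outcomes. The all-randomised analysis may be limited: the document does not say what NK data exist for the 34, the assay needs mononuclear cells from whole blood while the storage described follows separation into plasma and serum, and withdrawn consent may restrict use of some data. The result may look less certain.

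### Does reading NK activity at five effector:target ratios, with no ratio, summary or test named, leave the title endpoint open to a chance finding?

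*Combined protocol and SAP*

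**What the plan says.** The title announces an effect "on NK cell activity in hospitalized patients for rehabilitation", but no endpoint is labelled primary. Under NK Cell Activity, effector cells "were seeded into 96-well plates at ratios of 10:1, 5:1, 2.5:1, 1.25:1 and 0.625:1 with the K562 cells (target cell, T"), and percent cytotoxicity is then computed by a single formula. The section ends there. It names no ratio and no summary across ratios.

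Under Anthropometric Parameters and Blood Collection, days are attached to weight only: "Body weight during hospital stay was derived from the medical records on the first day and 14 days after consumption of each formula". The blood sentence gives no day: "Venous blood specimens were collected in EDTA-treated and plain tubes and centrifuged to obtain plasma and serum".

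The only statistical test in the document is a chi-square on diagnostic distribution (p = 0.100), under Participants. The document gives no between-arm test for NK activity, no alpha and no multiplicity rule.

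On timing, the first page reads "Date of the document : March, 2018" and "NCT number : In Progress (not assigned"). Participants adds "From August 2015 to March 2018, ninety-four patients were enrolled in this study" and "Results of this study were analyzed with sixty subjects, except for the dropouts".

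**The concern.** Five readings of one endpoint with no declared comparison are a familiar route to selective emphasis. If the arms could be declared different on whichever ratio came out best, the false-positive rate would exceed its nominal level.

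No bad faith is needed for trouble. Two analysts could each fix a reasonable rule in advance, one taking a single ratio and the other the mean of all five, and sometimes reach different verdicts on the same data. The document does not say whose verdict is the trial's.

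The timing adds to the worry. A plan that already counts dropouts and reports an analysed set cannot prove that an NK rule preceded the data, and it cites no registration number that might.

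**Working it through.** **What the text supports**

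- Counts agree: 94 − 34 = 60 analysed, and the diagnoses sum to 43 + 5 + 11 + 1 = 60.
- There is no planned sample size, power or alpha to reproduce.
- Enrolment ended in March 2018, the document carries the same month, and the analysis is undated. The dates alone therefore do not settle the order. The past-tense wording does: dropouts are counted, a p-value is given, and results are described as analysed.
- The weight days (first day and day 14) stand directly before the blood sentence, under a heading that covers both. A reader would probably infer the same days for blood, though the text does not say so.

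**Assumptions for the figures.** Two-sided 5% level, so 2.5% in favour of n3EN; five equally correlated readings with correlation ρ. For (b) and (c), also 30 per arm (60 split equally) and equal variances. None of these stands in the document.

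**(a) Any one ratio favouring n3EN counts as success, no true effect.** If the readings were independent: 1 − 0.975⁵ = 0.119. With correlation, the probability is 1 − ∫ Φ((1.96 − √ρ·g)/√(1 − ρ))⁵ φ(g) dg:

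| ρ | 0 | 0.5 | 0.7 | 0.9 | 0.95 | 0.99 |
|---|---|---|---|---|---|---|
| false claim | 11.9% | 9.1% | 7.4% | 5.1% | 4.2% | 3.2% |

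Counting significance in either direction, the independent case is 1 − 0.95⁵ = 22.6%, against a nominal 5%. All five wells come from one patient's mononuclear cells, so the right-hand columns are the relevant ones and independence is not credible.

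**(b) Two rules fixed in advance: one ratio, or the mean of five.** Share of simulated trials (40,000 per setting) in which exactly one rule is significant in favour of n3EN:

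| ρ | 0.5 | 0.7 | 0.9 | 0.99 |
|---|---|---|---|---|
| effect 0.736 SD at every ratio (80% power each) | 16% | 12% | 7% | 2% |
| no effect | 3.0% | 2.3% | 1.3% | 0.4% |

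This measures disagreement and is not an error rate. Each rule keeps its own 5% level. In a two-sided simulation (ρ from 0 to 1), one named ratio rejected in 4.9% to 5.2% of null trials and the mean of five in 4.8% to 5.2%.

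**(c) Is one rule plainly better?** The standardised effect on the mean, relative to one responding ratio, is (k/5)/√((1 + 4ρ)/5) when k ratios respond. Power by noncentral t with 58 df:

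| ρ | 0.5 | 0.7 | 0.9 |
|---|---|---|---|
| k = 5 | 0.951 | 0.895 | 0.832 |
| k = 2 | 0.304 | 0.250 | 0.214 |

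A single ratio has 0.80 power if it responds and misses the effect if it does not. Neither rule wins in all cases, so the choice between them is one of judgement.

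**The case for a change.** The strongest case for acting runs as follows. This is the combined protocol and analysis plan, yet it does not define the result on the outcome in its own title. The omission is certain. Stating the comparison costs only wording and uses values the assay has already produced. Because the text follows analysis, a dated disclosure of when the comparison was chosen would be worth having, and if the choice followed sight of results by arm, the NK conclusion should be called post hoc.

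The facts in that case stand: the ratio or summary, the sampling day, the test and the alpha are all absent. It is also true that this document cannot show that a rule came first.

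Three things limit it:

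- Nothing shows that ratios were tested separately, that one ratio could carry the conclusion, or that results by arm were seen before a rule was chosen.
- The protocol behind IRB approval 2015-0907 may contain a rule, and a pending NCT number does not show that the trial was unregistered elsewhere. Neither source is available here.
- Any replacement wording would have to leave the ratio or summary, the sampling day and the date blank and make the test conditional on whether a pre-feeding sample exists. Completing those blanks after analysis would describe the comparison; it could not make it pre-specified.

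The request for disclosure is therefore a fair point about how the NK result is reported and read.

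**Conclusion.** The gap is genuine, but no change to the plan follows. It is missing detail: no rule in the document is shown to produce a wrong result, and an analyst can fill the gap with any single ratio or summary fixed without sight of results by arm, which avoids the multiplicity problem.

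The size is modest under plausible conditions. The any-ratio rule, which the document does not state, would give a false claim in 5.1% to 3.2% of null trials at correlations of 0.9 to 0.99, against 2.5%. Two reasonable rules would disagree in 7% to 2% of trials when there is an effect and in 1.3% to 0.4% when there is none. These figures rest on an assumed two-sided 5% level and equal correlations. The disagreement rates also assume 30 per arm, equal variances and, where there is an effect, the same standardised effect at every ratio. With correlations of 0.5 to 0.7 the any-ratio figure would be 9.1% to 7.4%, but five wells from one sample make that less likely.

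Amending the text after analysis would gain little. It could not create pre-specification. Nor would naming a ratio guarantee a 5% level, because 34 of 94 randomised patients (36.2%) are outside the analysis whichever ratio is used. Readers should treat the NK result as confirmatory only if an earlier dated rule exists.

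### Does giving the NK assay's incubation time only as a minimum make the cytotoxicity values incomparable between runs?

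*Combined protocol and SAP*

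**What the plan says.** In the combined protocol and SAP, the NK Cell Activity section says that isolated mononuclear cells were plated with K562 targets at five effector-to-target ratios and kept at 37 °C "for more than 4 h. The cytolytic activities of NK cells were analyzed via the" kit described below. It gives no upper limit, tolerance or range. Other settings in the section are exact, for example blood that was "centrifuged for 20 min at 1800 rpm".

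Lysis was then measured with a commercial kit: "Assay Kit (Promega Co., Fitchburg, WI, USA) according to the manufacturer's instructions". The reference to the instructions belongs to the kit measurement. The instructions are not reproduced, so they cannot be read as fixing the incubation time.

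The result is a percentage. Its numerator is "Experimental-Effector Spontaneous-Target Spontaneous" and its denominator is "Target Maximum-Target Spontaneous". Time appears in neither.

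On numbers, the Participants section says: "Results of this study were analyzed with sixty subjects, except for the dropouts". Enrolment ran from August 2015 to March 2018. The document states no primary endpoint, no sample size calculation, no NK result, and no run or plate structure.

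**The concern.** Killing accumulates with time, so a percentage read after 6 h is not on the same scale as one read after 4 h. The effector and target controls correct for cells that leak or die unaided, and the maximum-release control sets the scale. None of them undoes a longer period of contact. Times of 4.1 h and 6 h would both satisfy the wording.

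NK activity is the outcome in the study's title, and recruitment lasted more than two and a half years. If the assays were done on fresh cells, they were spread over many runs. If contact times drifted from run to run, NK values would carry noise that has nothing to do with nutrition. If times also differed by arm, or by visit in a way that differed by arm, the group comparison would be biased.

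**Working it through.** The document has no stated figure to reproduce. The check has three parts: whether the formula absorbs killing time, how much noise a spread of times could add, and whether bias between arms is plausible. Every assay input below is an assumption. Only the 4 h floor, the formula and the 60 analysed patients come from the document.

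**1. Does the formula absorb killing time?** Assume true lysis of 20% at 4 h.

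- Constant-hazard killing, 1 − (1 − 0.20)^(t/4): 24.3% at 5 h, 28.4% at 6 h.
- Linear killing, 20% × t/4: 25.0% at 5 h, 30.0% at 6 h.

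Now pass the constant-hazard case through the document's formula, with assumed absorbances that let background grow with time: effector spontaneous 0.02t, target spontaneous 0.03t, target maximum 1.5. At 5 h:

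- effector spontaneous = 0.10 and target spontaneous = 0.15;
- experimental = 0.10 + 0.15 + 0.2434 × (1.5 − 0.15) = 0.5786;
- result = (0.5786 − 0.10 − 0.15) / (1.5 − 0.15) = 24.3%.

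The formula returns the 5 h value, not the 4 h value. It does not absorb time, so that part of the concern is right.

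**2. How much noise could a spread add?** Assume mean lysis 20%, between-patient SD 8 points, lysis proportional to time, and times uniform from 4 h to b and independent of patient. Then

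- CV of time = [(b − 4)/√12] / [(4 + b)/2];
- added variance as a fraction = CV² × (8² + 20²)/8² = 7.25 × CV²;
- effective n = 60 / (1 + added variance).

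The 8² term is needed because, under proportional lysis, the spread between patients stretches with time as well as the mean.

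| Times | CV² | Added variance | 60 patients worth |
|---|---|---|---|
| 4 to 4.5 h | 0.00115 | 0.8% | 59.5 |
| 4 to 5 h | 0.00412 | 3.0% | 58.3 |
| 4 to 6 h | 0.01333 | 9.7% | 54.7 |
| 4 to 8 h | 0.03704 | 26.9% | 47.3 |

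If NK activity were analysed as a change between two visits, with independent times at each, an SD of change of 8 and a single-visit SD of 8 (both assumed), the added fraction is 2 × (8² + 20²)/8² × CV² = 14.5 × CV². For 4 to 5 h that is 6.0%, and 60 patients are worth 56.6.

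The point at which added variance reaches 5% depends heavily on what is assumed. For a single measurement it is b = 5.34 h with SD 8, 4.83 h with SD 5 and 5.99 h with SD 12. For the change score above it is 4.91 h. The tolerable window therefore runs from about 0.8 h to 2.0 h, and the document gives no basis for choosing within it. No cut-off for concern can be taken from these figures.

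**3. Is bias between arms plausible?** Bias needs contact time to be related to arm. Allocation was by computer-generated lists, and the two formulas were identically packaged with no difference in appearance, texture or smell (Randomization and Intervention). Nothing there gives the laboratory a reason to time one arm's plates differently. Laboratory blinding and plate allocation are not described, so bias is not excluded, but nothing points to it.

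**The case for a change.** The strongest case for acting is that killing time is the one open-ended setting among precise ones, that it governs the outcome in the title, and that the formula cannot repair it. The reference to the kit's instructions does not help, because it attaches to the measurement step and supplies no time. A reader cannot confirm that NK values share one contact time, and another laboratory could not repeat the assay exactly. One sentence would settle the matter.

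All of these facts stand. They establish that the report is incomplete at this point. They do not establish that times varied, that the comparison is distorted, or that any analysis should differ. The exactness of the centrifuge setting says nothing about how steadily incubation was run. Adjusting for duration would need recorded times and material variation, and the document shows neither. With two visits there would also be two durations per patient, so a single duration covariate would not be well defined for a change score.

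**Conclusion.** The concern describes the text correctly but does not call for a change. The incubation time is given as a floor, and the cytotoxicity formula does not correct for it. A consistent time slightly above 4 h is a natural reading and would leave the values comparable. Under the assumptions above, a spread of up to half an hour costs less than 1% in the variance of a single measurement. A one-hour spread costs about 3%, or about 6% for a change score. Only a spread of several hours would cost much precision, and nothing in the document suggests one. Variation unrelated to arm would reduce power without invalidating the test, and no route to bias between arms is visible.

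The document is a past-tense account with enrolment complete, so the incubations themselves cannot be altered. What is missing is a laboratory detail that the team can supply from its records if asked. That is a matter of reporting and leaves the design and analysis as they are.
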